4.2 Safety Outcomes

4.2.1 Principal Safety Outcome

The principal safety outcome will be the time to first major bleeding within 12 months from randomization. Major bleeding is defined according to the International Society on Thrombosis and Haemostasis (ISTH) as overt bleeding that is associated with a decrease in the hemoglobin level ≥ 2 g/dL, leads to transfusion ≥ 2 units of packed red blood cells, occurs in a critical site, or contributes to death 1. The principal safety outcome will be independently adjudicated by a blinded CEC review. Non-hemorrhagic death will be considered a competing risk for this outcome.

4.2.2 Secondary Safety Outcome

The time to first clinically relevant non-major bleeding within 12 months will be evaluated and is defined per the ISTH as overt bleeding that does not meet the criteria for major bleeding but that is associated with the need for medical intervention, unscheduled contact with a physician, interruption or discontinuation of the study drug, or discomfort or impairment of activities of daily living 2. Like the primary safety outcome, this outcome will be assessed by the CEC, blinded to assigned treatments. All-cause death will be considered a competing risk for this outcome. We will also assess a composite outcome of major bleeding and clinically-relevant nonmajor bleeding. Non-hemorrhagic death will be considered a competing risk for these outcomes.

For all the outcomes, the last time contact date will be used for determining censoring.

5. Details of Randomization and Blinding

Subjects who are 18 years of age or older with provoked DVT and/or PE, have completed at least 3 months of therapeutic anticoagulation, have a low risk of bleeding, and have at least one enduring risk factor will be randomly assigned by computer in a 1:1 ratio to receive apixaban 2.5 mg orally twice daily or oral placebo for extended secondary prevention of VTE for a duration of 12 months.

This study will be conducted in a blinded fashion. To maintain blinding of study treatment, the active study drug and placebo will be matched for color, size and box. Subjects, investigators, members of any of the administrative and adjudicating committees, and the Sponsor's staff conducting the study, will not have access to individual subject treatment assignments.

An independent Safety Monitor has been selected for this study. The Safety Monitor is an expert in VTE and is distinct from the DMSB and Study Staff and will be available throughout the study to assess patient safety issues that may arise, objectively. The Safety Monitor will have the ability to break the blind of a study patient as the need arises (immediately, in real-time). If the Safety Monitor is unavailable because of travel, one of the Physician Study Investigators will serve as back-up.

6. Statistical Plan

6.1 Power Calculation

Our power calculation accommodates efficacy outcomes. This is an implementation of the power calculation method described in Section 14.12 (page 807) of Rosner (2006). The equation of power calculation based on 1:1 randomization is expressed as below:

$$Power = \Phi \left(\frac{\sqrt{m}|\lambda - 1|}{\lambda + 1} - Z_{1-\frac{\alpha}{2}} \right),$$

where m is the expected total number of events over both groups, n is the total sample size, p_E and p_c are the probabilities of event in treatment group and placebo group over the maximum time of the study, λ is postulated hazard ratios for the treatment over placebo.

We postulated the following anticipated parameters for the power calculation: a) by the end of follow up, the event rate of the placebo arm is 6% and there is 75% reduction rate with active treatment (low-intensity apixaban), i.e., the event rate of the placebo arm is 1.5%; b) the postulated hazard ratios for the treatment over placebo by 1-year follow-up ranges from 0.2-0.24. These anticipated parameters are based on previous studies ^{3,4}. In Figure 1, we provide the power analysis given certain sample size. The power under the significance of 0.05 is given for the total sample with 1:1 randomization ranging from 500-700. To achieve sufficient sample sizes needed for reach the power of 80%, we conservatively choose 600 patients to ensure the enough power.

[figure not shown]

Figure 1. The power calculation given the postulated hazard ratios and with 1:1 randomization. The red curve indicates the power of 80%.

6.2 Cohort Definition

In this section, we define a main cohort and four confirmatory cohorts for the analysis of efficacy and safety (**Table**).

Main Cohort (ITT): we will use the intention-to-treat (ITT) cohort since it maintains the original randomization scheme ("as randomized")⁵.

Confirmatory Cohort (MITT): the modified intention-to-treat (MITT) cohort consisting of all randomized patients who took at least one dose of the assigned treatment and did not undergo post-randomization exclusion.

Confirmatory Cohort (PP-1): Additional analyses will include a per-protocol (PP) population for subjects who took 80% of the study drug (or placebo).

Confirmatory Cohort (PP-2): Additional analyses will include a per-protocol (PP) population for subjects who took 80% of the study drug (or placebo) with censoring for either ISTH major bleeding or clinically relevant nonmajor bleeding event.

Confirmatory Cohort (Safety Cohort): In this cohort, we will only consider bleeding events (major bleed or clinically relevant non-major bleed) that occurred within 96 hours of taking a dose of the study drug (or placebo). The follow-up duration will be considered until the occurrence of a bleeding event or 96 hours after taking the last dose of the study drug (or placebo), whichever comes first.

6.2.1 Table. Analysis cohorts.

Analysis Set	Definition	Primary Efficacy-12-month recurrent symptomatic VTE	Primary Safety-12-month ISTH major bleeding
ITT	All randomized	Number of events Proportion Cumulative incidence Hazard ratio 95% confidence interval P-value	Number of events Proportion Cumulative incidence Hazard ratio 95% confidence interval
mITT	All randomized who took at least one dose of assigned treatment (apixaban or placebo) and did not undergo post-randomization exclusion	Number of events Proportion Cumulative incidence Hazard ratio 95% confidence interval	Number of events Proportion Cumulative incidence Hazard ratio 95% confidence interval
Per protocol without censoring for bleeding events	Subjects who took 80% of assigned treatment doses (apixaban or placebo)	Number of events Proportion Cumulative incidence Hazard ratio 95% confidence interval	Number of events Proportion Cumulative incidence Hazard ratio 95% confidence interval
Per protocol with censoring for bleeding events	Subjects who took 80% of assigned treatment doses (apixaban or placebo) with censoring for either ISTH major bleeding or clinically relevant nonmajor bleeding event	Number of events Proportion Cumulative incidence Hazard ratio 95% confidence interval	Number of events Proportion Cumulative incidence Hazard ratio 95% confidence interval
Safety set	Subjects who took at least one dose of the study drug (or placebo) until	Number of events Proportion Cumulative incidence Hazard ratio	Number of events Proportion Cumulative incidence Hazard ratio

	96 hours after the administration of the last dose of the study drug.	95% confidence interval	95% confidence interval P-value
--	---	-------------------------	---

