If a subject has a confirmed recurrent symptomatic VTE (DVT or PE), as deemed by the primary investigator, then the patient must discontinue study treatment and transition to the appropriate standard of care. The subject should remain in the study and should be followed in the same manner as a subject who has discontinued study treatment as described in the protocol.

Prohibited and/or Restricted Treatments

Prohibited Treatments:

The following medications or therapies are prohibited during the study treatment period:

- Potent inhibitors of CYP3A4 (e.g., azole antifungals [itraconazole and ketoconazole], macrolide antibiotics [clarithromycin and telithromycin], protease inhibitors [ritonavir, indinavir, nelfinavir, atazanavir, and saquinavir], and nefazadone)
- Aspirin > 81 mg/day
- Dual antiplatelet therapy such as concomitant (simultaneous) use of both aspirin and a thienopyridine (e.g., clopidogrel, ticlopidine)
- Other antithrombotic agents (e.g., UFH, LMWH, direct thrombin inhibitors, fondaparinux)
- GP IIb/IIIa inhibitors (e.g., abciximab, eptifibatide, tirofiban)

If treatment with a prohibited agent becomes necessary, study drug should be temporarily interrupted, and restarted as soon as possible following discontinuation of the prohibited medication or therapy.

Restricted Treatments:

The administration of the following agents in subjects on study drug should be done cautiously given the increased risk of bleeding. In such cases, consideration of interruption of the study drug may be warranted; this decision should be made after a careful assessment of the risks and potential benefits.

Examples:

- Chronic (> 3 months) daily NSAIDs. NSAIDs should not be administered in doses that exceed those in the approved label
- Cytotoxic/myelosuppressive therapy

In addition, if a subject is currently receiving an agent that is a potent inducer of CYP3A4 (e.g., rifampin), the investigator should carefully evaluate that subject's risk of thromboembolism, as the plasma concentration of apixaban may be lower than that in subjects not receiving a potent inducer of CYP3A4

Stopping Criteria

The DSMB will consider efficacy events, in addition to safety events, before making any study stopping recommendations to the principal investigator.

1. General Stopping Rules

- A. The DSMB, IRBs, regulatory authorities, or the Investigator may make recommendations to terminate the study if the safety and well-being of the subjects is in jeopardy.

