reduction (75%) in recurrent VTE as low-intensity rivaroxaban (10 mg daily) compared with low-dose aspirin (2). The 75% relative risk reduction was reported specifically for recurrent VTE and in the provoked VTE patient population, comparing rivaroxaban 10 mg daily versus low-dose aspirin. This relative risk reduction specifically pertains to our primary study outcome and our exact patient population and comes from a robust randomized controlled trial analysis. If anything, the reduction in the proposed study should be even greater since we propose a placebo-control instead of active (aspirin) control and we will be following our patients for 12 months, instead of allowing shorter follow-up as was reported in EINSTEIN CHOICE. Accordingly, assuming an estimated incidence in the placebo group of 6% at 12 months and a decrease in the primary outcome of 75% with apixaban 2.5 mg twice daily as compared with placebo, we calculated that we would need to enroll 279 patients in each group for the study to have 80% power to show the superiority of low-intensity apixaban over placebo, at a two-sided alpha level of 0.05. To account for patients who may be lost to follow-up or withdraw from the study, we will recruit 300 in each arm and 600 total.

EINSTEIN-CHOICE enrolled patients after a required 6 to 12 months of anticoagulant therapy. Our study requires that patients complete at least 3 months of anticoagulant therapy in accordance with current and widely-accepted evidence-based clinical practice guidelines (Eur Heart J. 2020; 41: 543–603, Chest. 2016;149:315-352, and Circulation. 2011;123:1788–1830). Data from the PADIS-PE study showed that the rate of VTE recurrence is higher closer in temporal proximity to the initial event, such that the recurrence rate is higher at 3-6 months after diagnosis than it is at 6-12 months (Couturaud F, et al. Six Months vs Extended Oral Anticoagulation After a First Episode of Pulmonary Embolism. JAMA. 2015;314(1):31-40). Accordingly, the anticipated event rate should be higher in our study than EINSTEIN-CHOICE and the resultant observed relative risk reduction is likely to be higher.

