Table. 8 Harvard Catalyst Biostatistics Program Consultant Sample Size Calculation Using Lower Limit of 95% Confidence Interval of Our Observational Cohort Estimate (performed by [name] using STATA).

Anticipated Event Rate = 8.2%

. power twoproportions .082 .0205, test(chi2) n(558)
 
Estimated power for a two-sample proportions test
 
Pearson's chi-squared test
 
Ho: p2 = p1 versus Ha: p2 != p1
 
Study parameters:
 
 alpha = 0.0500
 
 N = 558
 
 N per group = 279
 
 p1 = 0.0820
 
 p2 = 0.0205
 
Estimated power: power = 0.9111
 
Required N = 279 per group

Using this more conservative sample size calculation, we would aim to enroll 300 patients in each arm for a total trial population of 600.

Statistical Analysis Plan

For this study, we will calculate:

- 1) the 12-month frequency of major and clinically relevant non-major bleeding
- 2) the 12-month frequency of symptomatic recurrent VTE

The primary efficacy objective of this trial is to determine whether apixaban 2.5 mg twice daily is superior to placebo for the primary endpoint of symptomatic, recurrent VTE after 12 months of extended therapy. The analysis will include descriptive statistics of event rates and 95% CI, and risk difference and 95% CI. The Mantel-Haenszel statistic will be used to test this hypothesis formally. Superiority over placebo will be claimed for a dose if the Hochberg adjusted p-value is ≤ 0.05 and the RR is < 1 . The analysis will be supported by Kaplan-Meier curves. The primary efficacy outcome analysis will be intention-to-treat. We will also perform an on-treatment analysis.

The primary safety objective will be to determine whether apixaban 2.5 mg twice daily results in a statistically significant difference in major bleeding at 12 months (during the treatment period) compared with placebo. Analysis of incidence of these endpoints will be based on the safety analysis set. The analysis will include descriptive statistics of event rates and 95% CI, and risk difference and 95% CI. Hypotheses will be tested using Mantel-Haenszel statistic. The analysis will be supported by Kaplan-Meier curves of the time to first adjudicated major bleeding event. All bleeding analyses will be conducted on the safety dataset.

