6.4.2 Subgroup Analysis

The study will conduct subgroup analyses based on certain predetermined factors such as whether the patient has PE versus non-PE, age (65 years or older versus younger), sex (male versus female), chronic kidney disease (defined as presence or absence of eGFR<60 mL/min/1.72m²), atherosclerotic cardiovascular disease (present versus absent), baseline low-dose aspirin use (present versus absent), the number of provoking risk factors (2 or more versus less than 2), provoking factor of travel, and baseline aspirin use. The survival analysis within each subgroup will be repeated using the main cohort and tested in confirmatory cohorts, as needed. The p-value of the additive interaction effect between treatment and subgroup will be reported.

In case the subgroup analysis of baseline aspirin use indicates a relevant modification effect (the p-value for the additive interaction effect <0.05), the study will repeat the primary analysis by reporting the treatment effect of apixaban vs placebo with the adjustments for a) the use of aspirin and b) the interaction term.

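### SAP 6.2 ranks ITT above the Safety set for bleeding as well as efficacy, against the protocol and the SAP's own table, so bleeding subgroups and secondary bleeding outcomes land on ITT by rule or by default

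*Combined protocol and SAP*

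**What the plan says.** **SAP 6.2 (Cohort Definition).** The section opens "we define a main cohort and four confirmatory cohorts for the analysis of efficacy and safety". ITT is the main cohort. The Safety Cohort is listed as confirmatory and counts major or CRNM bleeds within 96 hours of a dose.

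**SAP Table 6.2.1.** It covers the two primary outcomes only. For major bleeding, every row lists events, hazard ratio and confidence interval, but only the Safety set row lists a p-value.

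**SAP 4.2.2 and 6.4.1.** CRNM bleeding and the major-plus-CRNM composite are defined as outcomes, and 6.4.1 describes how safety outcomes are analysed. Neither section assigns a cohort. Section 4.2.2 ends by censoring all outcomes at the last contact date.

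**SAP 6.4.2 (Subgroup Analysis).** "The survival analysis within each subgroup will be repeated using the main cohort and tested in confirmatory cohorts, as needed". Baseline aspirin use is among the subgroups.

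**Protocol (final version), Statistical Analysis Plan.** "All bleeding analyses will be conducted on the safety dataset". The safety population is patients with one or more doses, with no 96-hour window. Major bleeding is framed as occurring during the treatment period. An aspirin-stratified analysis of major bleeding is promised.

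**Protocol, Management of Recurrent Venous Thromboembolic Events.** After a confirmed recurrence, "then the patient must discontinue study treatment and transition to the appropriate standard of care", and the patient stays in the study.

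**The concern.** The rules for the trial's main harm conflict. The protocol assigns all bleeding to the safety dataset. SAP 6.2 demotes that set for safety as well as efficacy, and the SAP's own table then puts the formal major-bleeding test in the demoted set. The SAP gives no reason for departing from the protocol.

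Two things follow. The overall major-bleeding test would use on-treatment follow-up while its subgroups, including aspirin, use ITT follow-up. For CRNM and composite bleeding, an analyst could defend either set after seeing the data.

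The choice has a likely direction if apixaban causes bleeding. ITT adds off-drug time, which dilutes the apixaban arm. It also adds follow-up after recurrent VTE, which at the planning rates is concentrated in the placebo arm. If that care is anticoagulation (the case report form lists it as a treatment for DVT and PE), bleeds on open-label drug count against placebo. Both effects move the contrast toward the protocol's hypothesis of a similar bleeding rate.

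**Working it through.** **Plan figure.** The documents give no figure for bleeding or for any analysis set. The event rates used below come from the efficacy sample size, so that was checked first. With 6% vs 1.5%, "80% power to show the superiority of low-intensity apixaban over placebo, at a two-sided alpha level of 0.05" and a pooled chi-square test:

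n = [1.960 × √(2 × 0.0375 × 0.9625) + 0.842 × √(0.06 × 0.94 + 0.015 × 0.985)]² / 0.045² = (0.5266 + 0.2245)² / 0.002025 ≈ 278.6, so 279 per group. The stated 279 and power of 0.8005 reproduce.

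**Inputs from the documents.** 300 per arm ("To account for patients who may be lost to follow-up or withdraw from the study, we will recruit 300 in each arm"), VTE 6% vs 1.5%. Expected recurrences: 300 × 0.06 = 18 placebo, 300 × 0.015 = 4.5 apixaban.

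**Assumptions (not in the documents).**
- Recurrences occur on average at mid-year and lead to open-label anticoagulation.
- 10 to 25% of each arm stop drug at mid-year for other reasons (central 15%).
- Placebo major-plus-CRNM bleeding is 2 to 3% per year (central 2.5%).
- Bleeding on open-label anticoagulant is 5 to 12% per year (central 8%).
- Off-drug bleeding equals the placebo rate.

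**Formula.** Expected ITT bleeds = on-drug years × arm rate + off-drug years × placebo rate + open-label years × open-label rate. Each arm has about 300 person-years, so the ratio of bleeds is the ratio of rates. Truncation at first bleed, deaths and loss are ignored.

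**Central case, true on-drug ratio 1.5.** Off-drug years are 45 × 0.5 = 22.5 per arm. Open-label years are 18 × 0.5 = 9 and 4.5 × 0.5 = 2.25.
- Placebo: 268.5 × 0.025 + 22.5 × 0.025 + 9 × 0.08 = 6.71 + 0.56 + 0.72 = 8.00
- Apixaban: 275.25 × 0.0375 + 22.5 × 0.025 + 2.25 × 0.08 = 10.32 + 0.56 + 0.18 = 11.06
- Apparent ratio: 11.06 / 8.00 = 1.38

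**Ends of the range, true 1.5.**
- 25% stops, 2% and 12% rates: placebo 253.5 × 0.02 + 37.5 × 0.02 + 9 × 0.12 = 6.90; apixaban 260.25 × 0.03 + 37.5 × 0.02 + 2.25 × 0.12 = 8.83; ratio 1.28
- 10% stops, 3% and 5% rates: placebo 276 × 0.03 + 15 × 0.03 + 9 × 0.05 = 9.18; apixaban 282.75 × 0.045 + 15 × 0.03 + 2.25 × 0.05 = 13.29; ratio 1.45

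| True on-drug ratio | Apparent ITT ratio |
|---|---|
| 1.0 | 0.95 (central) |
| 1.5 | 1.28 to 1.45 (central 1.38) |
| 2.0 | 1.66 to 1.91 |

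**Dilution alone.** Without open-label time, the apparent ratio is (1 − f) × HR + f, where f is the off-drug share of apixaban time. With f from 5 to 30%, 2.0 becomes 1.95 to 1.70 and 1.5 becomes 1.475 to 1.35. A ratio of 1.0 stays at 1.00, so the 0.95 above comes entirely from the open-label assumption.

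**Against sampling error.** In the central case SE(log ratio) = √(1/8.00 + 1/11.06) = 0.46. The 95% interval around 1.38 is about 0.56 to 3.4. The shift is ln(1.5/1.38) = 0.083, or 0.083 / 0.46 = 0.18 SE.

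**Major bleeding.** The protocol's background cites 0.4% on low-dose rivaroxaban and 0.3% on aspirin: 300 × 0.004 = 1.2 and 300 × 0.003 = 0.9 bleeds. Chance swamps any dilution there.

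**The case against.** A reader might infer more than the documents support.

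- **That ITT is primary for all bleeding.** It is not. Table 6.2.1 puts the only major-bleeding p-value in the Safety set, as the protocol requires.
- **That the SAP chooses ITT for CRNM and composite bleeding.** It is silent. The Safety Cohort definition names CRNM bleeds, and nothing in the SAP withdraws the protocol's rule. ITT is only the default reading of the main-cohort label.
- **That these results will understate an apixaban excess.** This presumes an excess. The protocol hypothesises a similar rate and reports that, in the cited placebo-controlled extension trial, major and CRNM bleeding at this dose resembled placebo. ITT bleed counts also cannot be lower than Safety set counts; only the contrast between arms can shrink.
- **That the calculated dilution measures SAP against protocol.** It compares the SAP's 96-hour set with ITT. The protocol's safety population has no such window, so a dosed patient who switches after a recurrence remains in it. The treatment-period phrase is attached to major bleeding only.
- **That major and composite bleeding could not be read together.** The table also reports ITT hazard ratios for major bleeding.

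It is also fair that 6.4.2 allows other cohorts as needed and does not name bleeding outcomes. But 6.4.1 applies the survival analysis to safety outcomes, so bleeding subgroups fall under the main-cohort rule, and a discretionary second analysis does not settle which result leads. These points limit the claim; the conflict between the passages remains.

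**Conclusion.** The concern holds as a conflict of stated rules, not as an error in the primary safety test. SAP 6.2 disagrees with the protocol and with Table 6.2.1 on which set leads for bleeding. Bleeding subgroups go to ITT by rule; CRNM and composite bleeding go there by default.

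Following 6.2 and 6.4.2 can pull those contrasts toward or below 1. The size is conditional on bleeding, stopping and switching rates the documents do not give, and on care after recurrence being anticoagulation. Under the ranges shown, a true 1.5 appears as 1.28 to 1.45. At the central values (1.5 − 1.38) / 0.5 = 24% of the excess is lost. That is well inside sampling error, so it would rarely change a conclusion alone. The practical exposure is in CRNM and composite bleeding, where more events are expected than for major bleeding. The open choice of set on the main harm justifies a correction at moderate priority.

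**What to change.** 1. In SAP 6.2, state that ITT is primary for efficacy outcomes and the Safety set is primary for every bleeding outcome (major, CRNM and their composite), with ITT bleeding supportive. Remove the confirmatory label from the Safety set.
2. Add CRNM and composite bleeding to Table 6.2.1.
3. In 6.4.2, name ITT for efficacy subgroups and the Safety set for bleeding subgroups, including baseline aspirin use.
4. Reconcile the SAP's 96-hour window with the protocol's definition of one or more doses, and with the sentence in 4.2.2 that censors all outcomes at last contact. Changing the labels alone would leave this mismatch in place.

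The cost is SAP wording. No new data are needed, and ITT bleeding results are still reported.
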